[figure not shown]
Does Negative Pressure Wound Therapy with Instillation Reduce the Bioburden of Infections?

Sponsor: KCI NCT04826965

Duke IRB#: Pro00105056

- **1) Protocol Title:** Does Negative Pressure Wound Therapy with Instillation Reduce the Bioburden of Infections?
- **2)** Purpose of the Study: The purpose of this study is to compare the microbiologic burden and need for further operative debridement of patients undergoing primary surgical debridement of infected tissue, soft tissue abscesses, or traumatic wounds, between patients treated with traditional VAC therapy and those treated with instillation with VAC Veraflo therapy with Cleanse Choice.

Primary endpoint: Bacterial bio-burden as measured by quantitative microbial PCR prior to debridement, immediately following initial debridement, after 2 days of VAC veraflo (or conventional VAC) therapy, and at the time of repeat operative debridements, if needed. We will use the MicroGen PCR platform (DBA Microgen Diagnostics, LLC, Lubbock, TX.) to report on the bacterial burden (reported on a log scale of bacteria per gram) present at the time of debridement.

Exploratory endpoint: Number of operative debridements required prior to reconstruction, number of days until final reconstruction, number of days until decision is made by surgeon that further debridements are no longer necessary, length of hospital stay, wound surface area.

3) Background & Significance:

Plastic, orthopedic, vascular, and general surgeons commonly encounter infections. These may be post-traumatic (e.g. from a laceration while cooking or at the site of a fracture), embolic (seeding of infection from another source), or due to inoculation (e.g. from a contaminated needle used for intravenous illicit drug use). Regardless of the etiology, these patients present with complex problems that often require repeat debridement prior to reconstruction. Their hospital stays are lengthy, painful (in terms of pain from debridement and dressing changes), and expensive (based on the number of repeat operations required to debride infected tissue). The results of the initial surgical debridement are often uncertain- patient and disease factors contribute to the extent and recurrence of the disease and often surgeons will empirically schedule "second looks" to return to the operating room for a repeat debridement/inspection of the wound prior to performing a reconstruction, in order to avoid experiencing a failed reconstruction due to inadequate debridement. A possible cause for failure of reconstruction is the microbial bioburden present in the open wound. We hypothesize that the continuous irrigation as well as the cycles of wound/exudate disruption afforded by the V.A.C Veraflo technology with Cleanse Choice Dressing will reduce the microbial bioburden and possibly the need for operative debridement by allowing for around-the-clock non-excisional debridement and irrigation.

4) Design & Procedures:

Prospective randomized trial. Two arms, 20 patients in each arm. Study team expects to consent/enroll 60 patients in order to achieve 40 subject for evaluation due to voluntary opt-out, inability to return to OR for "second look" debridement on day 2, medical instability preventing further debridement, etc.

Day 0 - (Prior to surgery):

- Consent, randomization, enrollment

Day 1 (day of first operative debridement):

- Patient arrives in the operating room, anesthesia is induced. The extremity is prepared and draped in standard fashion.
- A small piece of tissue (on the order of grams) is excisionally debrided in standard surgical fashion. This tissue **specimen 1** is placed into the plastic specimen collection cup provided by MicroGen, labeled, and the plastic bag containing the cup is sealed. The cardboard box provided in the kit is sealed and, being pre-addressed and pre-paid, is sent to MicroGen in Texas. **The patient receives a random number for use with the MicroGen sample and no identifying information (Name, age, MRN) is sent to MicroGen.**
- Debridement proceeds in standard surgical practice. The prior specimen collection does not rob the lab of tissue that the surgeon, in his/her judgment seeks to send for microbiology culture or pathology.
- At the conclusion of debridement/irrigation, a repeat small piece of tissue **specimen 2** is excised and sent to MicroGen in the same manner.
- At the conclusion of debridement, based on randomization, a wound vac or wound vac with cleanse choice dressing, track pad duo, and saline irrigation is applied. The wound is dressed in standard fashion according to the sugeon's preference (e.g. splint, ACE wrap, etc.).
- Patient emerges from anesthesia, and heads to recovery/floor or ICU as planned.

Day 1 until day 2:

- Negative pressure wound therapy or negative pressure wound therapy with irrigation proceeds automatically, 24/7

Day 2 (second operative debridement):

- Patient arrives in the operating room, anesthesia is induced. The extremity is prepared and draped in standard fashion.
- A small piece of tissue (on the order of grams) is excisionally debrided in standard surgical fashion. This tissue **specimen 3** is placed into the plastic specimen collection cup provided by MicroGen, labeled, and the plastic bag containing the cup is sealed. The cardboard box provided in the kit is sealed and, being pre-addressed and pre-paid, is sent to MicroGen in Texas. **The patient receives a random number for use with the MicroGen sample and no identifying information (Name, age, MRN) is sent to MicroGen.**
- Debridement proceeds in standard surgical practice. The prior specimen collection does not rob the lab of tissue that the surgeon, in his/her judgment seeks to send for microbiology culture or pathology.

- This next step is completely up to the surgeon. Additional debridement, reconstruction, fracture fixation, reconstruction, closure, repeat wound vac. Additional samples are not collected.
- Patient emerges from anesthesia, and heads to recovery/floor or ICU as planned.

Future debridements, if performed:

- Done at Day 5 (+/- 1 day). This is an optional step as many patients will not require additional debridement. Tissue samples will be sent at the time of the third surgery, whether it is a debridement, reconstruction, or other procedure.
- Tissue collection at the start of each further surgery for MicroGenPCR. In the event that wounds are dirty/infected and require repetitive debridements, we may collect as many as n additional samples for n additional operative debridements to track the bioburden over time.

Demographics and data to be collected on participants:

Patient name, age, gender, MRN, height, weight, type of injury, mechanism of injury, concurrent fracture involved with the wound, major vascular injury, prior debridements before presentation, date/time of injury, date/time of ED or hospital presentation, date/time of irrigation in ED (if performed), date/time of preliminary surgery, date/time of additional debridements, reconstructions, number of days until closure/reconstruction, number of days to decision is made that debridement is complete, comorbidities: [diabetes, smoking, steroid use, radiation], lab values: [CBC, BMP, albumin], vital signs. Surgical details: type of anesthesia, surgeon, surgical service, operative time, anesthesia time, type of debridement, level of debridement, whether a concurrent operation was performed, wound area/area of debridement, whether a drain was placed, volume of irrigation, pre-op intra-op and post-op antibiotics. Type of tissue debrided and sent for our samples (and location within the wound). If debridement is abandoned, e.g. if surgeon decides only an amputation will cure this wound.

ICU stay, blood transfusion, mechanical ventilation postoperatively. Date of discharge. Several of these variables, including when the decision is made to reconstruct, may require searching the EMR after discharge. For example, a patient may be sent home with a plan for a nurse to change dressings for weeks at home. The patient may present to clinic after discharge and the surgeon examines the wound then decides to schedule wound closure/reconstruction (e.g. skin graft, flap, etc).

We will follow the patients for the duration of care.

5) Selection of Subjects:

Inclusion criteria:

- Patients age 18 years or older who have an injury or infection for which surgical debridement (in the operating room) followed by VAC application is planned.
- Able to provide informed consent.

Page 4 of 7

- Speak and read English.
- Patients may be immunosuppressed, either through nature of disease or due to medication.
- Patients may be on systemic antibiotics or topical antimicrobials.
- Patients may present with exposed bone or joint space as part of either the debridement or traumatic injury.

Exclusion criteria:

- Patients on therapeutic anticoagulation to treat DVT/PE, atrial fibrillation, etc, for which we would include warfarin, therapeutic heparin or low-molecular-weight heparin, direct oral anticoagulants (e.g. rivaroxaban, dabigatran).
 - Most of these patients are on prophylactic anticoagulation to lower the risk of a DVT (e.g. heparin or enoxaparin subcutaneous injections). We would still like to include those patients in our study. These drugs are given to many hospitalized patients due to their immobility and are not prescribed to the same patients once they are safely living at home again. Additionally, many patients are on aspirin for the coronary prevention factor and we do not even usually hold this prior to surgery (even if someone wanted to, it takes days of waiting to reverse the platelet effects and these are acute wounds/infections). We would also like to include patients on aspirin or clopidogrel (anti-platelet agents), for example.
- 6) Subject Recruitment and Compensation: A maximum of 60 subjects will be consented in order to achieve 40 evaluable subjects. Duke subjects will be introduced by their healthcare team and if interested in participating, will be given more information by the research team. Potential subjects will be screened in the ED or Hospital and identified by an investigator or a member of the research team. An investigator will confirm eligibility criteria and a member of the site study team will notify the sponsor of a potential candidate for the study after the subject has been consented.

There is no subject compensation planned for this study.

7) Consent Process: Subjects will be introduced to the study by their physician and then the study team will provide additional information and consent if subjects are interested in participating in the study. See iRIS consent section for additional consent details. Patients will be approached after permission is granted by a member of the care team.

These infections or injuries may present at "inopportune times", e.g. early hours of the morning and be posted for surgery to commence in the next several hours to days. If a patient is interested in participation, they will have the opportunity to discuss research up to the time they are entered into pre-op holding.

- **8)** Subject's Capacity to Give Legally Effective Consent: Only subjects able to give legally effective consent will be permitted to participate in this study.
- **9) Study Interventions:** Instillation within the wound vac

From the manufacturer (Veraflo with cleanse choice):

The unique three-layer design of the V.A.C. VERAFLO CLEANSE CHOICE™ Dressing promotes a wound cleansing option that facilitates removal of thick exudate material, such as fibrin, slough and thick wet exudate, and other infectious material, to provide a wound cleansing option for clinicians when surgical debridement must be delayed or is not possible or appropriate.

From the manufacturer (Conventional VAC):

When used on open wounds, they are intended to create an environment that promotes wound healing by secondary or tertiary (delayed primary) intention by preparing the wound bed for closure, reducing edema, promoting granulation tissue formation and perfusion and by removing exudate and infectious material. Open wound types include: chronic, acute, traumatic, subacute and dehisced wounds, partial-thickness burns, ulcers (such as diabetic, pressure or venous insufficiency), flaps and grafts.

- **Risk/Benefit Assessment:** We do not yet know if the instillation affects the time to healing or the number of debridements required. Both the wound vac and vac with instillation are standard-of-care interventions, not currently known to present any additional risk to subjects. The variable that most directly affects the patient is the length of wound therapy and/or number of operative debridements required.
- Costs to the Subject: There will be no additional costs to subjects for participating in this study. The two methods are both standard of care. The study drug/device will be provided at the standard cost to the patient. These are patients who were already selected to be managed with negative pressure (wound vac) wound therapy, the difference will be the type of vac dressing that they receive.

12) Data Analysis & Statistical Considerations:

Primary endpoint: Bacterial bio-burden as measured by quantitative microbial PCR prior to debridement, immediately following initial debridement, after 2 days of VAC veraflo (or conventional VAC) therapy, and at the time of repeat operative debridements, if needed. We will use the MicroGen PCR platform (DBA Microgen Diagnostics, LLC, Lubbock, TX.) to report on the bacterial burden (reported on a log scale of bacteria per gram) present at the time of debridement.

Exploratory endpoint: Number of operative debridements required prior to reconstruction, number of days until final reconstruction, number of days until

Page 6 of 7

decision is made by surgeon that further debridements are no longer necessary, length of hospital stay, wound surface area.

[name] to do analysis using JMP (SAS) software. Will use t-test for log scale of bacteria per gram.

Power analysis for a one-way ANOVA with 2 groups was conducted to determine a sufficient sample size using an alpha of 0.05, a power of 0.80, and a large effect size (f = 0.40) Based on the aforementioned assumptions, the desired sample size is 25.52. Original funding called for 60 patients, but funding agency subsequently retracted their offer to cover indirect costs, so the sample size was decreased to 40 patients total as the grant now must absorb the indirect costs.

13) Data & Safety Monitoring:

All adverse events related to the study will be signed off on by the PI and reported to the IRB in accordance with Duke and HIPAA policies.

Privacy, Data Storage & Confidentiality: Any data that is stored in paper or non-digital format will be locked in a file cabinet within a controlled access office. The office will be locked when not in use by the study team. All electronic study information will be stored on the secure Surgery Server in the IRB folder for this study with access limited only to the study team. All study information will be stored in accordance with the RDSP for this study.

Confidentiality of subject data will be ensured by de-identification of subject data. During data collection, subject identifiers and relevant data elements will be recorded in the database. Then, study-specific identification numbers will be assigned to each subject. Prior to dissemination of any information in this database beyond the DUMC's secure servers or firewall, all identifiers will be stripped from the database and data will only be referenced by the study-specific identification numbers.

The adequacy of the Research Data Security Plan will be evaluated and approved by the Surgery CRU and IT personnel prior to study conduct.

Any publications or presentations that result from this research will not identify any subjects individually, and will present data in aggregate form only.

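### Randomisation is listed before surgery, the arm is first used after the first debridement and specimen 2, and nothing in the plan conceals it in between

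*Combined protocol and SAP*

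**What the plan says.** Section 4 (Design & Procedures) puts "Consent, randomization, enrollment" under Day 0, before surgery. The Day 1 steps are then listed in this order:

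1. Specimen 1 is taken.
2. "Debridement proceeds in standard surgical practice".
3. Specimen 2: "At the conclusion of debridement/irrigation, a repeat small piece of tissue" is excised and sent to the laboratory.
4. The dressing: "At the conclusion of debridement, based on randomization, a wound vac or wound vac with cleanse choice dressing" and its accessories are applied.

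The only coding step concerns what goes to the laboratory: "The patient receives a random number for use with the MicroGen sample and no identifying information" is sent with it. The list of data to be collected, also in section 4, includes the type, level and area of debridement, the irrigation volume, and "Type of tissue debrided and sent for our samples (and location within the wound".

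Sections 2 and 12 define the primary endpoint as bacterial burden on a log scale at several times. These include the time before debridement (specimen 1), the time just after it (specimen 2) and the time after two days of therapy (specimen 3). Section 12 plans a t-test. It states no adjustment and does not say which time point is tested.

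**The concern.** Specimens 1 and 2 are taken before either device touches the wound, so a systematic arm difference in them cannot be a device effect. If the arm is known at that stage, a difference could arise in two ways:

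- **Debridement.** Its extent is left to usual practice. Section 3 hypothesises that instillation provides continuing non-excisional debridement, so someone who knows the arm could have a reason to debride more or less.
- **Choice of tissue.** The plan sets no fixed rule for where in the wound the specimens are taken.

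The first route leaves a real difference in starting burden. It can persist to Day 2, where an unadjusted t-test cannot tell it from a device effect. The second distorts specimens 1 and 2 themselves, which are endpoint measurements. Randomisation protects against neither, because both happen after it.

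**Working it through.** **What the text supports.** Randomisation is placed on Day 0, and its first stated use is the dressing step on Day 1, listed after specimen 2. Between the two, the documents mention no sealed or delayed disclosure, no masking of the operating team, no independent sampler, and no fixed rule for extent of debridement or sampling site. The random number on the sample concerns the laboratory, not the operating room.

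**Figures in the plan.** The plan gives none on this point. Its one sample-size figure, 25.52, reproduces as the number per group for a two-sided 0.05 test with 80% power and d = 2 × 0.40 = 0.80. It plays no part below.

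**Illustration for the plan as written.**

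- From the plan: 20 per arm, alpha 0.05, t-test.
- Assumed: a two-sided test applied to specimen 3; no device effect; knowledge of the arm shifts post-debridement burden by s standard deviations; a fraction c of that shift carries over to specimen 3.
- Bias in SD units of specimen 3: b = s × c.
- Noncentrality: b / √(2/20) = b / 0.3162, with 38 degrees of freedom and critical value 2.024.
- False-positive rate: the probability that a noncentral t with that parameter exceeds 2.024 in absolute value.

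| Shift s | Carry-over c | Bias b | Noncentrality | Rejects |
|---|---|---|---|---|
| 0 | any | 0 | 0 | 5.0% |
| 0.2 | 0.3 | 0.06 | 0.190 | 5.4% |
| 0.2 | 0.5 | 0.10 | 0.316 | 6.1% |
| 0.2 | 0.7 | 0.14 | 0.443 | 7.2% |
| 0.5 | 0.3 | 0.15 | 0.474 | 7.5% |
| 0.5 | 0.5 | 0.25 | 0.791 | 12.0% |
| 0.5 | 0.7 | 0.35 | 1.107 | 19.0% |

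**What adjustment for specimen 2 does.** This was simulated by ANCOVA of specimen 3 on arm and specimen 2, with 200,000 trials per cell. True burden B has SD 1, specimen 2 is B plus error, and specimen 3 is c × B plus noise, with total SD 1.

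- *The arm shifts the real burden by 0.5 SD.* The adjusted test rejects in 5.0-7.8% over c from 0.3 to 0.7 and specimen 2 reliability from 1.0 to 0.6. Adjustment removes most of the bias.
- *The arm shifts only which tissue is taken as specimen 2, by 0.5 SD, with true burden equal.* The unadjusted test stays at about 5%. With reliability 1.0, the adjusted test rejects in 7.6%, 13.7% and 30.4% at c = 0.3, 0.5 and 0.7. Adjustment brings in a bias that was not there before.

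So adjustment is safe only if specimen 2 was taken before the arm was known.

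**The case against.** The strongest reply is that no harm is shown. The dressing step ties use of the allocation to the end of debridement, which fits a list made on Day 0 and opened only when the dressing is chosen. That stands: a reader might infer that the surgeon knows the arm during debridement, and the documents do not say so. They support only that the time of disclosure is not stated and that nothing prevents early disclosure.

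A reader might also infer that the plan names the surgeon as the person who chooses the specimen tissue. It does not. The specimens are described in the passive, and the remark about surgical judgment concerns tissue for culture or pathology. That the surgical team chooses is the natural reading, but an inference.

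The plan also records debridement type, level and area, irrigation volume, and tissue type and location. An arm difference in these could therefore be examined. That is a partial safeguard: it helps to detect a difference but does not prevent one.

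Two further readings go too far:

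- **The 30% figure as an error rate of this plan.** It arises only if adjustment for specimen 2 is added while the arm is known, and the plan states no such adjustment.
- **Early randomisation as the cause of the expected losses.** The plan says "A maximum of 60 subjects will be consented in order to achieve 40 evaluable subjects", but of the three reasons section 4 names, failure to return on Day 2 and instability preventing further debridement fall after the dressing. Only voluntary opt-out could clearly fall earlier. The gap may also be short, since for patients interested in taking part "they will have the opportunity to discuss research up to the time they are entered into pre-op holding". No figure can be given for losses in that gap.

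Finally, the dressings differ visibly, so the arm becomes known in any case. That is true from the dressing onward, but the stage before it can be protected.

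**Conclusion.** The point holds as a gap in concealment that is cheap to close, not as a demonstrated bias. The arm is assigned before surgery and first used after the first debridement and specimen 2, and the documents conceal it at no stage in between. Two measurements in the primary endpoint, and the starting burden for the Day 2 comparison, are therefore open to influence by knowledge of the arm.

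The size is unknown and may be zero. For the plan as written, the assumed range gives false-positive rates of 5% with no shift, 5.4-7.2% with a 0.2 SD shift and 7.5-19% with a 0.5 SD shift. The 19% is the extreme corner of that range. Shift, carry-over and the use of specimen 3 as the tested value are all assumptions. The change should be made; confidence is medium, because whether the arm is disclosed early is not known.

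**What to change.** 1. Keep consent on Day 0. Open a concealed allocation (sealed envelope or electronic) only after specimen 2 is taken and just before the dressing is applied. The sequence must be one in which the next assignment cannot be predicted.
2. Count patients as randomised from that moment, and list earlier exits as consented but not randomised.
3. Compare specimen 3 between arms adjusted for log specimen 2, and state that this is the comparison the test addresses.

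Make changes 1 and 3 together. Adjusting for specimen 2 while the arm is known could add bias if the arm influences which tissue is taken.

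Cost: protocol wording, plus envelopes or an electronic list. Specimen 2 is already collected, so no extra patients, specimens or procedures are needed. Both dressing kits must be in the OR, and someone already present must open the allocation during the operation, including off hours.

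Limit to state in the protocol: because the dressings differ visibly, the sampling of specimen 3 and losses after the dressing are not protected by this change.

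### No rule fixes where in the wound the primary-endpoint tissue is taken, and whoever cuts the Day 2 specimen can know the arm

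*Combined protocol and SAP*

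**What the plan says.** All references are to the combined protocol and SAP.

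- **Timing of randomization.** Section 4 lists "Consent, randomization, enrollment" under Day 0, before any specimen is taken.
- **Specimens 1 and 3.** The instruction is the same on both operating days: "A small piece of tissue (on the order of grams) is excisionally debrided in standard surgical fashion". On Day 2 this comes at the start of the operation, before further debridement.
- **Specimen 2.** "At the conclusion of debridement/irrigation, a repeat small piece of tissue" is excised and sent in the same way. Nothing ties it to the site of specimen 1, and nothing ties specimen 3 to the site of specimen 2.
- **The arms.** After specimen 2, "based on randomization, a wound vac or wound vac with cleanse choice dressing, track pad duo, and saline irrigation is applied".
- **What is recorded.** The data list in Section 4 includes "Type of tissue debrided and sent for our samples (and location within the wound".
- **What the laboratory sees.** Samples travel under a random number and "no identifying information (Name, age, MRN) is sent to MicroGen".
- **Analysis.** Section 12 gives the endpoint as "reported on a log scale of bacteria per gram" and the method as "Will use t-test for log scale of bacteria per gram". Tissue type, location and baseline burden play no part in it.

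The documents do not say who picks the piece of tissue or when the allocation is revealed to the surgeon, and they describe no blinding of anyone.

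**The concern.** The trial compares what a single piece of tissue shows in each arm. If burden differs from place to place within a wound, the reading depends partly on which piece is cut. The wounds range from abscesses to trauma with exposed bone or joint, and the plan itself records tissue type and location, so it evidently expects both to vary.

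Specimen 3 is the first measurement after treatment. It comes from a wound that has just carried one of two recognizably different devices. A person who can know the arm, and who has no site rule to follow, may lean towards cleaner or dirtier tissue in one arm without intending to. The t-test cannot separate that lean from an effect of instillation.

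Coding at the laboratory comes too late to help, because the selection is made before the sample is boxed. Adjusting later for the recorded Day 2 location is not a reliable cure either, because that location was itself chosen after allocation.

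**Working it through.** **1. Who can know the arm, specimen by specimen**

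- Specimens 1 and 2: randomization has taken place on Day 0, but the allocation is first acted on after specimen 2, when the device is applied. The arm may be known; the plan does not say.
- Specimen 3: the device applied on Day 1 is in use until Day 2 and differs visibly between arms. The arm can be known, and no step conceals it from the person taking the sample.

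**2. The plan's own sample size**

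Inputs from Section 12: alpha 0.05, power 0.80, f = 0.40, two groups. For two equal groups d = 2f = 0.80. The noncentral F calculation, with noncentrality f² × N, gives 25.52 per group (51.05 in total). The stated 25.52 is therefore reproduced as a per-group figure. At the planned 20 per arm (Section 4), power at d = 0.80 is 0.693.

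**3. What a selection shift would do**

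The documents give no within-wound variance and no bias size, so the shift b, in SD units, is assumed. The test is taken as two-sided and applied to the Day 2 value; Section 12 states neither.

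With n = 20 per arm there are 38 degrees of freedom, and the noncentrality is b × √(n/2) = b × √10.

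No true difference:

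| Assumed shift b | Noncentrality | Rejection rate |
|---|---|---|
| 0 | 0 | 0.050 |
| 0.2 | 0.632 | 0.095 |
| 0.3 | 0.949 | 0.152 |
| 0.4 | 1.265 | 0.234 |

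True d = 0.80 with the shift running against it (net difference 0.80 − b):

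| Assumed shift b | Net d | Power |
|---|---|---|
| 0 | 0.80 | 0.693 |
| 0.2 | 0.60 | 0.456 |
| 0.3 | 0.50 | 0.338 |
| 0.4 | 0.40 | 0.234 |

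**4. Does matching the site also improve precision?**

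Write the Day 2 log burden as arm mean + patient effect + site effect + error. If the surgeon may designate any site for specimen 2 and specimen 3 is taken beside it, the site effect still varies from patient to patient as before. The between-patient SD of the Day 2 value is unchanged, and power stays at about 0.69; a simulation with site choice contributing 20% or 30% of the variance agreed. A gain appears only if specimen 2 enters the analysis, as a change score or a covariate, because the site effect shared by the two specimens can then be removed.

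**The case against.** The strongest reply has four parts.

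*The inference may be unfair.* A reader might infer that the tissue is chosen freely by a surgeon who knows the arm throughout. The documents do not say that. They do not name who selects the piece, and the allocation is not used until after specimen 2. This stands for specimens 1 and 2. For specimen 3 the visible device, the absence of any blinding and the absence of a site rule are enough to say that the arm can be known.

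*The bias is hypothetical.* Nothing in the documents shows that a surgeon can steer a PCR count by choosing tissue, or in which direction. This also stands. The tables show how the test responds to a shift, not that a shift of that size will occur.

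*There are safeguards.* Samples are coded, tissue type and location are recorded, and specimen 3 has a standard time, before further debridement. These deserve credit: timing is aligned between arms and site differences can at least be described. None of them governs which tissue is taken.

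*Fixing the site may not buy power.* A reader might infer that a site rule would recover some of the power lost by stopping at 20 per arm. For the planned t-test on the Day 2 value it would not, as step 4 shows. Nor would an analysis restricted to pairs from matching sites be a sound check. Whether a pair matches is decided on Day 2 by someone who can know the arm, so the restriction conditions on a choice made after allocation and also discards patients.

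**Conclusion.** The concern holds as an unguarded route to bias, chiefly at specimen 3. The plan leaves the site of the primary-endpoint sample open at a moment when the arm can be known, and neither the coding nor the recording closes that gap. Selection could produce an apparent effect or mask a real one.

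Size and direction cannot be derived from the documents. The rates of 9.5%, 15% and 23% rest on assumed shifts of 0.2, 0.3 and 0.4 SD, 20 evaluable patients per arm, and a two-sided 5% t-test on the Day 2 value. They do not estimate this trial's error rate. The documents do not support a claim that biased sampling has occurred or will occur, or that standardizing the site alone would raise power above about 0.69.

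The change should be made because it is cheap and needs no extra specimen. The gap does not invalidate the design.

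**What to change.** Add to Section 4:

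1. The allocation is opened only after the Day 1 debridement is finished, specimen 2 is taken, and its site and tissue type are recorded by diagram or photograph.
2. Specimen 3 is taken at the start of the Day 2 operation, before further debridement, next to the recorded site and from the same tissue type where the surgeon judges this feasible.
3. Deviations are recorded with the reason and reported by arm. All patients stay in the primary analysis whether or not the sites matched.

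The investigators still choose the site; the rule only requires that it be settled before the arm is known and then repeated. The sampler on Day 2 is still not blinded and the feasibility clause leaves some discretion, which is why deviations are reported by arm.

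If better precision is also wanted, that is a separate change to Section 12: prespecify a change-score analysis or one adjusted for specimen 2.

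The cost is a short amendment and a field on the data form. The allocation workflow also changes, since the assignment must stay closed until the end of the Day 1 debridement. Where specimen 3 is cut is guided in advance, and a fixed site may sometimes miss the most contaminated area, though under the same rule in both arms. No extra specimen or staff is needed.
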